To assess understanding, we will ask participants 3 questions: (1) the approved indication of tivozanib, (2) the most common serious side effect associated with treatment, and (3) the recommended dose of treatment. Answers to all 3 questions can be found in the standard patient leaflet. Information about the drug's indication is also included in both key information sections; information about the most common serious side effect is presented in the EMA's proposed key information section with qualitative statements. Participants randomized to the key information section with both qualitative statements and quantitative data will receive 2 additional questions: one asking them to identify the difference in overall survival between tivozanib and standard treatment, and another asking about the difference in serious side effects.

Next, all participants will be asked a series of questions to assess their satisfaction with the information presented in the version of the patient leaflet they were assigned. Before ending the survey, we will ask participants for information about their demographics: their age, sex, highest level of educational attainment, and personal experience with cancer (whether themselves, an immediate family member or close friend had been diagnosed with cancer).

Primary outcome

The primary outcome of the study is participants' expectations about the drug's benefits and side effects. We selected tivozanib as the test treatment because it is representative of many recently approved cancer drugs. Tivozanib is not curative for advanced kidney cancer and, at the time of approval, it demonstrated no additional overall survival or quality of life benefit relative to standard treatment (sorafenib). Owing to the lack of information about drug benefits in the standard patient leaflet and the limited information quantifying side effects, we hypothesized that participants would overestimate the benefits and underestimate the side effects of tivozanib.¹⁴

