Note: Left panel shows the standard patient leaflet for tivozanib (control); upper right panel shows the EMA's proposed key information section with qualitative statements; lower right panel shows the key information section containing both qualitative and quantitative information.

----- end of page-----

Section A: Previous experience using the patient leaflet

1. If you are currently prescribed or have ever been prescribed a medicine, how often do you read the patient leaflet?
 - Often
 - Sometimes
 - Rarely
 - Never
2. If you are currently prescribed or have ever been prescribed a medicine, how often do you talk to your doctor about the information you see in the patient leaflet?
 - Often
 - Sometimes
 - Rarely
 - Never

----- end of page-----

Section B: Participants' expectations and understanding of treatment using the patient leaflet

Imagine that your doctor prescribes you a new medicine. When you pick up the medicine from the pharmacy, you read the patient leaflet included in the box.

This patient leaflet is for a medicine called Fotivda. You can zoom in and scroll through every page of the leaflet. You can also download it here: [Fotivda.pdf](#)

You will be shown the patient leaflet for Fotivda on every page for the next few questions, along with an option to download the leaflet. Please use the information in the leaflet to answer the questions.

----- end of page-----

3. This first question is practice. Scroll to section 3 of the leaflet and find the first word.
 - Always **[correct]**
 - Serious
 - Patient
 - Chance

----- end of page-----

4. What is Fotivda used for?
 - To treat adults with breast cancer
 - To treat adults with heart failure
 - To treat adults with advanced kidney cancer **[correct]**
 - To treat adults with advanced lung cancer
 - Not sure

----- end of page-----

5. Does Fotivda cure advanced kidney cancer?
 - Definitely yes
 - Probably yes
 - Probably no
 - Definitely no

----- end of page-----

6. Do people with advanced kidney cancer live longer when treated with Fotivda?
 - Definitely yes
 - Probably yes
 - Probably no
 - Definitely no

----- end of page-----

7. Do people with advanced kidney cancer feel better when treated with Fotivda?

- Definitely yes
- Probably yes
- Probably no
- Definitely no

----- end of page-----

8. Compared to standard treatment, how long did people given Fotivda live? **[Key information table group]**

- 6 months **less** than people given standard treatment

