- 2.6 months **less** than people given standard treatment **[correct]**
- About the same as people given standard treatment
- 2.6 months **longer** than people given standard treatment
- 6 months **longer** than people given standard treatment
- Not sure

----- end of page-----

9. Overall, how large are the benefits of Fotivda?

- Very large
- Large
- Moderate
- Small
- Very small to none

----- end of page-----

10. To confirm that the survey is functioning correctly, please select 'Standard treatment', below.

- Fotivda
- Advanced kidney cancer
- Standard treatment **[correct]**
- Neither Fotivda or standard treatment

----- end of page-----

11. Compared to standard treatment, how common were serious side effects with Fotivda? **[Key information table group]**

- 22% **less** common than with standard treatment
- 6% **less** common than with standard treatment **[correct]**
- About the same as standard treatment
- 6% **more** common than with standard treatment
- 22% **more** common than with standard treatment
- Not sure

----- end of page-----

12. What is the most common serious side effect of Fotivda?

- Rapid or irregular heart beat
- High blood pressure **[correct]**

- Diarrhoea
- Muscle spasms
- Not sure

----- end of page-----

13. How concerning are the side effects of Fotivda?

- Extremely concerning
- Very concerning
- Somewhat concerning
- Not at all concerning

----- end of page-----

14. Do you think the benefits of Fotivda outweigh the side effects?

- Definitely yes
- Probably yes
- Probably no
- Definitely no

----- end of page-----

15. What is the recommended dose of Fotivda during the first 3 weeks of treatment? **[All groups]**

- One 890 microgram capsule daily
- One 1340 microgram capsule daily **[correct; answer in section 3 of PIL]**
- Two 1340 microgram capsules daily
- Two 890 microgram capsules daily
- Not sure

----- end of page-----

Section C: Participants' satisfaction with the patient leaflet

You're almost done. What was your experience of using the patient leaflet for Fotivda?

16. Was it easy to find information about Fotivda using the leaflet?

- Very easy
- Easy
- Difficult
- Very difficult

17. Was it easy to understand the information?

- Very easy
- Easy
- Difficult
- Very difficult

Please rate your agreement with the following statements.

18. The leaflet helped me think about the benefits of Fotivda.

- Strongly agree
- Agree
- Disagree
- Strongly disagree

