19. The leaflet helped me think about the side effects of Fotivda

- Strongly agree
- Agree
- Disagree
- Strongly disagree

20. The leaflet helped me think of questions I would like to ask my doctor

- Strongly agree
- Agree
- Disagree
- Strongly disagree

21. Overall, did you find the patient leaflet for Fotivda:

- Very helpful
- Helpful
- Unhelpful
- Very unhelpful

----- end of page-----

Section D: Demographics

Thank you for taking the time to respond to this survey. These last 5 questions are to help us better understand you.

22. How old are you?

- 18 to 24
- 25 to 44
- 45 to 64
- 65 and older

23. What is your sex?

- Male
- Female
- Other

24. What is the highest level of education that you have completed?

- Less than 5 GCSE's A* to C (or equivalent i.e., level 1 diploma/ certificate /BTEC /NVQ)
- 5 or more GCSE's A* to C (or equivalent i.e., level 2 diploma/ certificate/ BTEC/ NVQ, O-Levels)
- 2 or more A-Levels (or equivalent i.e., level 3 diploma/ certificate/ BTEC)
- Undergraduate degree or higher

25. What is your approximate yearly income?

- Less than £20,000
- £20,000 to £34,999
- £35,000 to £44,999
- £45,000 and above

26. Have you, a close friend, or immediate family member (i.e. your partner, parents, siblings, or children) ever been diagnosed with cancer? (Select as many that apply)

- I have been diagnosed (currently, or in the past)
- An immediate family member has been diagnosed with cancer
- A close friend has been diagnosed with cancer
- To my knowledge, none of my close friends or family, or myself, has been diagnosed with cancer

----- end of page-----

----- end of survey message -----

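### Survey questions 8 and 11, asked only in the quantitative arm, precede the perceived benefit and harm ratings, so contrasts with that arm mix the leaflet with an extra prompt

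*Combined protocol and SAP*

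**What the plan says.** The Procedure section states: "Participants randomized to the key information section with both qualitative statements and quantitative data will receive 2 additional questions". One concerns the survival difference and the other the difference in serious side effects. In survey Section B they are question 8 ("Compared to standard treatment, how long did people given Fotivda live") and question 11 ("Compared to standard treatment, how common were serious side effects with Fotivda"), both tagged for the key information table group.

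The ratings put to all arms are question 9 ("Overall, how large are the benefits of Fotivda"), question 13 ("How concerning are the side effects of Fotivda") and question 14 ("Do you think the benefits of Fotivda outweigh the side effects"). Under Secondary outcomes, these three make up the perceived-magnitude outcome, analysed as proportions compared between groups. Statistical analysis plans chi-square tests, with logistic models adjusted for demographics. Nothing in the document describes a random question order, a matched task for the other two arms, or an analysis that allows for the extra questions.

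**The concern.** Randomisation supports a statement about the leaflet only if the leaflet is all that differs between arms. Here one arm also has to find specific benefit and harm figures shortly before rating benefit and harm. Everyone in that arm gets the extra questions and nobody else does, so arm and prompt coincide completely and no covariate adjustment can separate them.

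At stake is the reading of the perceived-magnitude results for the quantitative format, which is the design the investigators developed themselves. A difference could come from the table, from being made to look up two of its rows, or from both.

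**Working it through.** **Order of the questions.** As printed in survey Sections B and C:

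| Question | Content | Asked of | Role |
|---|---|---|---|
| 5, 6, 7 | Cure, live longer, feel better | All | Primary outcome |
| **8** | Survival difference | **Quantitative arm only** | Extra comprehension item |
| 9 | Size of benefits | All | Perceived magnitude |
| 10 | Attention check | All | Quality control |
| **11** | Difference in serious side effects | **Quantitative arm only** | Extra comprehension item |
| 12 | Most common serious side effect | All | Understanding |
| 13 | Concern about side effects | All | Perceived magnitude |
| 14 | Benefits outweigh side effects | All | Perceived magnitude |
| 15 | Recommended dose | All | Understanding |
| 16 to 21 | Experience of the leaflet | All | Satisfaction |

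- Question 9 follows one arm-specific question (8). Questions 13 and 14 follow both.
- Questions 5 to 7 precede question 8, so none of the 3 primary contrasts is exposed.
- Questions 12 and 15 are factual look-ups and are unlikely to be affected.
- Carry-over to satisfaction is possible. It is most plausible for question 18 ("The leaflet helped me think about the benefits of Fotivda") and question 19 ("The leaflet helped me think about the side effects of Fotivda").

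**Exposed comparisons.** The plan specifies pairwise contrasts only for the primary outcome. Assuming the same pairs for the three ratings, there are 3 items × 3 pairs = 9 comparisons. Of these, 3 × 2 = 6 include the quantitative arm and 3 × 1 = 3 do not.

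**The plan's sample size (context only; not disputed).** Inputs from Statistical analysis: 60% versus 50%, 90% power, two-sided alpha 0.05/3 = 0.0167.

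- n = [z(1−α/2)·√(2p̄q̄) + z(0.90)·√(p₁q₁ + p₂q₂)]² / d² = [2.394 × 0.7036 + 1.282 × 0.7000]² / 0.10², which gives 667 per group.
- With a continuity correction this becomes 687, in line with the planned 700. Power at 700 is 91.5%.

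**What difference would be called significant.** Smallest observed difference by uncorrected chi-square, 700 per arm. The comparator rate is an assumption, because the documents give none for these items. Entries are decrease / increase, in percentage points.

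| Comparator rate | p<0.05 | p<0.0167 |
|---|---|---|
| 10% | 3.0 / 3.4 | 3.6 / 4.3 |
| 30% | 4.7 / 5.0 | 5.7 / 6.1 |
| 50% | 5.3 / 5.3 | 6.4 / 6.4 |

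Example: 350/700 versus 313/700 is a difference of 37/700 = 5.3 points, with z = 1.98. A difference of 36/700 gives z = 1.93, which falls short of 1.96.

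**If the prompt alone shifted the answers.** Suppose the leaflet has no effect and the prompt lowers the quantitative arm's proportion by s. The probability of a significant result is approximately Φ[(s − z(1−α/2)·SE₀)/SE₁], where SE₀ is the pooled and SE₁ the unpooled standard error. For s = 5 points from 50%: (0.050 − 1.96 × 0.02669)/0.02666 = −0.087, which gives 46.5%.

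| Assumed shift | p<0.05, base 50% / 30% | p<0.0167, base 50% / 30% |
|---|---|---|
| 3 points | 20% / 24% | 10% / 13% |
| 5 points | 47% / 55% | 30% / 38% |
| 10 points | 97% / 99% | 92% / 97% |

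The shifts and base rates are assumptions. The 0.0167 threshold is planned for the primary outcome and is shown only as a stricter alternative.

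**The case against.** The strongest reply is that the extra questions add no information. Both answers are already in the quantitative leaflet's table, the leaflet stays on screen for each question, all arms are told to use it, and no feedback on answers is described. Shared questions also cover much of the same ground: 6 and 7 raise survival and how people feel before question 8, and 12 raises serious side effects immediately before 13. For question 14 the keyed answers (shorter survival, fewer serious side effects) pull in opposite directions, so a net shift is hard to predict. The significance thresholds would be the same without questions 8 and 11 and do not measure the problem.

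Much of this stands. The prompt's effect may be small, its direction is unknown, and the thresholds give scale only. Question 6 makes question 8 an addition to an earlier prompt rather than a new one. Carry-over to satisfaction is a possibility, not a finding.

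None of it removes the asymmetry. Having a table available is not the same as being required to find a given row. Nor does question 8 merely repeat question 6: it asks for a comparison with standard treatment and keys the 2.6-month shortfall as correct, without the table's caution that the difference may be chance. Before question 11 no question in any arm covers side effects, and question 12 asks for the commonest serious effect rather than a comparison between treatments. That the other arms cannot answer 8 and 11 justifies asking them in one arm, but not placing them ahead of shared outcomes.

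**Conclusion.** The concern holds. For questions 9, 13 and 14, contrasts with the quantitative arm estimate the leaflet together with arm-specific prompting. That is 6 of 9 comparisons if all pairs are tested. The primary outcome and the control versus qualitative contrast are not affected.

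The existence and position of the extra questions are plain from the document. Whether they move the ratings, by how much and in which direction cannot be derived from it. The bias is therefore potential and confined to secondary outcomes. It is still worth correcting, because it is avoidable at almost no cost and the planned analysis cannot remove it afterwards.

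**What to change.** Move questions 8 and 11 to after question 21, just before the demographic items, with the leaflet still displayed, and state this position in the Procedure section. Every item compared between arms then follows an identical sequence. Placing them after question 14 would protect the three perceived-magnitude items but leave the satisfaction items following an unequal sequence.

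The cost is reordering two survey questions, with no added participants or items. The two comprehension items would be answered later in the survey, and the line opening Section C that tells participants they are nearly finished may need a small edit.

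If data are already collected, report the asymmetry as a limitation of the quantitative-arm contrasts on questions 9, 13 and 14 and on the satisfaction items, and describe those differences as effects of the leaflet plus the additional questions.
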